8. ADVERSE EVENTS MANAGEMENT

8.1. Definitions of Adverse Events, Adverse Reactions, and Serious Adverse Events

8.1.1. Adverse Events

An adverse event (AE) is any untoward medical occurrence in a clinical study subject administered a medicinal product, which does not necessarily have a causal relationship with the treatment. An AE can therefore be any unfavorable and/or unintended sign, symptom, or disease temporally associated with the use of a medicinal product, whether or not considered related to the medicinal product. AEs may also include pre- or post-treatment complications that occur as a result of protocol specified procedures, lack of efficacy, overdose, drug abuse/misuse reports, or occupational exposure. Preexisting events that increase in severity or change in nature during or as a consequence of participation in the clinical study will also be considered AEs.

An AE does not include the following:

- Medical or surgical procedures such as surgery, endoscopy, tooth extraction, and transfusion. The condition that led to the procedure may be an adverse event and must be reported.
- Pre-existing diseases, conditions, or laboratory abnormalities present or detected before the screening visit that do not worsen
- Situations where an untoward medical occurrence has not occurred (e.g., hospitalization for elective surgery, social and/or convenience admissions)
- Overdose without clinical sequelae (see Section 7.5.1)
- Any medical condition or clinically significant laboratory abnormality with an onset date before the consent form is signed and not related to a protocol-associated procedure is not an AE. It is considered to be pre-existing and should be documented on the medical history CRF.

8.1.2. Serious Adverse Events

A serious adverse event (SAE) is defined as an event that, at any dose, results in the following:

- Death
- Life-threatening (Note: The term “life-threatening” in the definition of “serious” refers to an event in which the subject was at risk of death at the time of the event; it does not refer to an event that hypothetically might have caused death if it were more severe.)
- In-patient hospitalization or prolongation of existing hospitalization
- Persistent or significant disability/incapacity

- A congenital anomaly/birth defect
- A medically important event or reaction: such events may not be immediately life-threatening or result in death or hospitalization but may jeopardize the subject or may require intervention to prevent one of the other outcomes constituting SAEs. Medical and scientific judgment must be exercised to determine whether such an event is a reportable under expedited reporting rules. Examples of medically important events include intensive treatment in an emergency room or at home for allergic bronchospasm; blood dyscrasias or convulsions that do not result in hospitalization; and development of drug dependency or drug abuse. For the avoidance of doubt, infections resulting from contaminated medicinal product will be considered a medically important event and subject to expedited reporting requirements.

8.1.3. Clinical Laboratory Abnormalities and Other Abnormal Assessments as Adverse Events or Serious Adverse Events

Laboratory abnormalities without clinical significance are not recorded as AEs or SAEs. However, laboratory abnormalities (eg, clinical chemistry, hematology, and urinalysis) that require medical or surgical intervention or lead to SOF/VEL interruption, modification, or discontinuation must be recorded as an AE, as well as an SAE, if applicable. In addition, laboratory or other abnormal assessments (eg, electrocardiogram, x-rays, vital signs) that are associated with signs and/or symptoms must be recorded as an AE or SAE if they meet the definition of an AE or SAE as described in Sections 8.1.1 and 8.1.2. If the laboratory abnormality is part of a syndrome, record the syndrome or diagnosis (eg, anemia), not the laboratory result (ie, decreased hemoglobin).

For specific information on handling of clinical laboratory abnormalities in this study, please refer to Section 3.4.

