7. TOXICITY MANAGEMENT

7.1. Dose Modification Due to Toxicity

7.2. Group 1: Subjects administered SOF/VEL

There is no option for dose reduction or modification of SOF/VEL

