7.3. Group 2: Subjects administered SOF/VEL+ RBV

Dose modification for subjects administered SOF/VEL+RBV should be performed according to the prescribing information.

Dose reduction of SOF/VEL is not permitted.

Table 7-1. Ribavirin Dose Modification Guideline for Coadministration with SOVALDI

Laboratory Values	Reduce Ribavirin Dose to 600 mg/day ^a If:	Discontinue Ribavirin If: ^b
Hemoglobin in patients with no cardiac disease	<10 g/dL	<8.5 g/dL
Hemoglobin in patients with history of stable cardiac disease	≥2 g/dL decrease in hemoglobin during any 4 week treatment period	<12 g/dL despite 4 weeks at reduced dose

a The daily dose of ribavirin is administered orally in two divided doses with food.

b Once ribavirin has been withheld due to either a laboratory abnormality or clinical manifestation, an attempt may be made to restart ribavirin at 600 mg daily and further increase the dose to 800 mg daily. However, it is not recommended that ribavirin be increased to the original assigned dose (1000 mg to 1200 mg daily).

If RBV is permanently discontinued, SOF should also be discontinued.

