9.1.2. Primary Endpoints

The primary efficacy endpoint is SVR12 (HCV RNA < LLOQ 12 weeks after cessation of study treatment regimen) in the Full Analysis Set (FAS).

The primary safety endpoint is any AE that led to permanent discontinuation of study drug.

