9.2. Analysis Conventions

All individual subject data will be listed as measured. All statistical summaries and analyses will be performed using SAS[®] software (SAS Institute, Cary, North Carolina, USA).

The study drug in this study is SOF/VEL or SOF/VEL +RBV. Last dose of study drug refers to the last dose of any of the study drugs in a treatment group and will be used in the definition of treatment-emergent AEs and laboratory abnormalities as well as the efficacy endpoints of SVR at various post-treatment time points.

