#### 7.1.6. Summaries of Adverse Events and Deaths

A brief high-level summary of TEAEs will show, by treatment group, the number and proportion of subjects who had the following: (1) any AE, (2) any AE of Grade 3 or above, (3) any AE of Grade 2 or above, (4) any treatment-related AE, (5) any treatment-related AE of Grade 3 or above, (6) any treatment-related AE of Grade 2 or above, (7) any SAE, (8) any treatment-related SAE, (9) any AE that led to premature discontinuation of any study drug, (10) any AE that led to modification or interruption of any study drug, (11) any AE that led to premature discontinuation of SOF/VEL, (12) any AE that led to interruption of SOF/VEL, (13) any AE that led to discontinuation of RBV, (14) any AE that led to modification or interruption of RBV, and (15) all deaths.

Summaries (number and percentage of subjects) of TEAEs (by SOC and PT) will be provided by treatment group using the safety analysis set as follows:

- All AEs
- AEs of Grade 3 or above
- AEs of Grade 2 or above
- All treatment-related AEs
- Treatment-related AEs of Grade 3 or above
- Treatment-related AEs of Grade 2 or above
- All SAEs
- All treatment-related SAEs

- AEs leading to premature discontinuation of any study drug
- AEs leading to modification or interruption of any study drug

Multiple events will be counted once only per subject in each summary. The SOC's will be presented alphabetically and the PT's within each SOC will be presented by descending order of the total frequencies. In summaries by severity grade, the most severe grade will be used for those AEs that occurred more than once in an individual subject during the study.

In addition to the above summary tables, TEAEs will also be summarized by PT only, in order of descending incidence within the overall treatment group for:

- All AEs
- AEs that occurred in at least 5% of subjects within any treatment group
- AEs of Grade 3 or above
- All treatment-related AEs
- All SAEs
- AEs leading to premature discontinuation of any study drug
- AEs leading to modification or interruption of any study drug
- AEs leading to premature discontinuation of SOF/VEL
- AEs leading to interruption of SOF/VEL
- AEs leading to modification or interruption of RBV
- AEs leading to discontinuation of RBV

Data listings, with a variable indicating whether the event is treatment emergent, will be provided for the following:

- All AEs
- AEs of Grade 3 or above
- SAEs
- Deaths

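### The laboratory-to-AE recording rule names SOF/VEL but not ribavirin, so tables of AEs leading to RBV modification or interruption may undercount in Group 2

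*Protocol*

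**What the plan says.** Protocol 8.1.3 starts from a default: "Laboratory abnormalities without clinical significance are not recorded as AEs or SAEs". It then lists what must be recorded. Laboratory abnormalities that need medical or surgical intervention, or that "lead to SOF/VEL interruption, modification, or discontinuation must be recorded as an AE". Laboratory or other abnormal findings "that are associated with signs and/or symptoms must be recorded as an AE or SAE", provided they meet the definition in 8.1.1 or 8.1.2. A last sentence says to record the syndrome or diagnosis rather than the laboratory result, with anaemia as the example.

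On dose changes, Protocol 7.2 says for Group 1: "There is no option for dose reduction or modification of SOF/VEL". Protocol 7.3 bars SOF/VEL dose reduction in Group 2 as well. RBV is different. Table 7-1 gives haemoglobin triggers for reducing and discontinuing it, and its footnote on restarting begins "Once ribavirin has been withheld due to either a laboratory abnormality or clinical manifestation". Protocol 5.4.4 also lets the investigator modify doses for anaemia or other reasons. Protocol 7.3 ends by saying SOF should stop if RBV is permanently discontinued.

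On analysis, Protocol 9.2 counts RBV as study drug in Group 2: "Last dose of study drug refers to the last dose of any of the study drugs in a treatment group". Protocol 9.1.2 states: "The primary safety endpoint is any AE that led to permanent discontinuation of study drug". The high-level summary in SAP 7.1.6 includes "any AE that led to modification or interruption of RBV", and a parallel item covers any study drug. The matching tables are 15.11.5.3, 15.11.5.4 and 15.11.5.7.

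**The concern.** The recording trigger covers the whole regimen in Group 1 but one of two drugs in Group 2. Modification, one of the three actions it lists, has almost nothing to act on for SOF/VEL, which cannot be reduced. It is the usual action for RBV, which the rule leaves out. This reads like a drafting slip.

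Safety and tolerability of each regimen is a primary objective, and haemoglobin-driven RBV change is a main expected tolerability cost of Group 2. If some of these changes carry no AE, the tables meant to show that cost understate it in one group. Capture would also vary by site for reasons unrelated to the drug.

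**Working it through.** **1. Figures in the plan.** No plan figure rests on this rule. The related background rates reproduce: in ASTRAL-4, 27/87 = 31.0% had RBV modified or interrupted due to AEs, and 9/87 = 10.3% stopped RBV due to AEs while continuing SOF/VEL.

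**2. Three Group 2 cases under 8.1.3.** Take a subject with no symptoms whose haemoglobin crosses a Table 7-1 threshold, and who receives nothing beyond the RBV change.

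| Action | SOF/VEL trigger met? | Symptom route met? | AE mandatory? |
|---|---|---|---|
| RBV reduced | No | No | Only if the site calls the change a medical intervention |
| RBV held, then restarted | No | No | Same |
| RBV permanently stopped | Yes, if SOF also stops as 7.3 says | No | Yes |

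The gap is therefore confined to reductions and temporary holds.

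**3. Does other text close it?**
- Medical intervention is not defined.
- The anaemia sentence governs which term to use. It does not say that an entry is required.
- 8.1.3 refers to Section 3.4 for handling laboratory abnormalities, but Section 3.4 has no haemoglobin criterion.
- Under Appendix 3, a value just below 10 g/dL (the Table 7-1 reduction threshold without cardiac disease) can be as low as Grade 1 in an HIV-positive subject and Grade 2 in an HIV-negative one. A site could judge it not clinically significant.

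**4. Where the loss would appear.** Tables 15.11.5.3, 15.11.5.4 and 15.11.5.7 count AEs only. Exposure duration (SAP 4.2.1) ignores temporary interruptions.

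**5. What the other tables recover.** Haemoglobin by visit, graded abnormalities, and subjects below 10 and 8.5 g/dL (Table 15.11.6.1.5.2) do not depend on AE entry. Adherence (SAP 4.2.2) is tablets taken divided by tablets prescribed at baseline: 6 × 84 = 504, or 5 × 84 = 420. Consider a change to the 600 mg/day of Table 7-1 (3 tablets), assuming that no other tablet is missed:
- From the start of Week 5: (28×6 + 56×3)/504 = 336/504 = 66.7%, or (28×5 + 56×3)/420 = 308/420 = 73.3%. Both fall below the 80% cut.
- From the start of Week 9: (56×6 + 28×3)/504 = 420/504 = 83.3%, or (56×5 + 28×3)/420 = 364/420 = 86.7%. Both stay above it.

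Adherence thus registers RBV reductions indirectly, depends on their timing, and cannot separate them from missed tablets.

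**6. Size.** Missing subjects = M × f. M is the number of Group 2 subjects with an asymptomatic, laboratory-only RBV reduction or hold, and f is the share that sites do not record. The documents give neither. With f assumed anywhere from 0 to 1, the loss runs from none to all M. In Group 1 it is 0, because no RBV is taken.

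**The case against.** The strongest reply is that 8.1.3 does not say laboratory abnormalities are recorded only when a trigger is met. It excludes those without clinical significance and lists cases that must always be recorded. A clinically significant fall outside the list can still be an AE under 8.1.1. A fall that makes an investigator cut RBV is hard to call insignificant, and the section's own example is anaemia. The SAP plans RBV-specific rows, so the sponsor evidently expects AEs to be linked to RBV action. The eCRF completion guidelines, which are not among the documents, may say more. All of this stands, and it makes the undercount a possibility rather than a certainty. It does not make recording mandatory, and it leaves the outcome to site judgement.

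Two stronger readings do not hold. A reader might infer that the primary safety endpoint is undercounted. It counts permanent discontinuation, and when RBV stops for good, Protocol 7.3 brings SOF with it, which meets the trigger. That protection is not firm: 7.3 says SOF rather than SOF/VEL, Protocol 3.7 permits stopping RBV alone when a partner is pregnant, and SAP Table 15.11.5.8 tabulates RBV discontinuation separately. The partner-pregnancy case is not itself a laboratory event; it shows only that the link is not universal. A reader might also infer that the toxicity disappears from the report. It does not, given the laboratory tables, adherence, the drug administration listing (16.2.5.1) and the SVR12 table by dose modification (15.9.4.3). What is missing is a safety table of how many Group 2 subjects had RBV changed, and why.

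Finally, no between-group test or difference is planned. Any distortion is in a descriptive reading of two columns, not in a formal comparison.

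**Conclusion.** The point holds in limited form. As written, the rule leaves an arm-specific, site-dependent gap for asymptomatic haemoglobin falls that lead only to an RBV reduction or temporary hold. The tables of AEs leading to modification or interruption of RBV, or of any study drug, may undercount in Group 2 only.

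The size is unknown. A reader might be tempted to start from the 31.0% in ASTRAL-4 or the 9.8% in the SOF+RBV group of ASTRAL-2 and assume that a share of these would be lost. The documents do not support this. Both rates count changes already attributed to AEs, so they are not a base from which events go missing; if anything, they show that such changes were recorded as AEs before. The ASTRAL-4 subjects also had CPT class B cirrhosis, whereas this trial targets compensated cirrhosis and excludes haemoglobin below 10 g/dL at screening. No document gives the share that is laboratory-only.

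The conclusion assumes that sites follow the protocol text and that the eCRF guidelines do not already extend the rule to RBV. A correction is worthwhile because it is nearly free and concerns a primary objective.

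**What to change.** In Protocol 8.1.3, change the object of the trigger from SOF/VEL to any study drug, so that it reads: *interruption, modification, or discontinuation of any study drug (SOF/VEL or RBV)*. Carry the same wording into the eCRF completion guidelines.

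Reconcile three places on whether RBV can stop alone: the last line of Protocol 7.3, the partner-pregnancy provision in Protocol 3.7, and the SAP's separate table of AEs leading to RBV discontinuation. This is a request for consistency and takes no position on which clinical rule is right.

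Optionally, add one descriptive safety row in SAP 4.2 or 7.1.6 from the study drug administration data: number and percent of Group 2 subjects with RBV reduced, interrupted or stopped, with the reason where collected. That result would not depend on AE entry.

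The cost is one phrase and, if wanted, one table row from administration data already planned for collection. The Group 2 AE rate may look slightly higher. No dose or stopping rule is altered.

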8.2. Assessment of Adverse Events and Serious Adverse Events

The investigator or qualified subinvestigator is responsible for assessing AEs and SAEs for causality and severity, and for final review and confirmation of accuracy of event information and assessments.

8.2.1. Assessment of Causality for Study Drugs and Procedures

The investigator or qualified subinvestigator is responsible for assessing the relationship to IMP therapy using clinical judgment and the following considerations:

- **No:** Evidence exists that the adverse event has an etiology other than the IMP. For SAEs, an alternative causality must be provided (eg, pre-existing condition, underlying disease, intercurrent illness, or concomitant medication).
- **Yes:** There is reasonable possibility that the event may have been caused by the study drug.

It should be emphasized that ineffective treatment should not be considered as causally related in the context of adverse event reporting.

The relationship to study procedures (eg, invasive procedures such as venipuncture or biopsy) should be assessed using the following considerations:

- **No: Evidence** exists that the adverse event has an etiology other than the study procedure.
- **Yes:** The adverse event occurred as a result of protocol procedures, (eg., venipuncture)

8.2.2. Assessment of Severity

The severity grading of AEs will be assessed as Grade 1, 2, 3, or 4 using the GSI Grading Scale for Severity of Adverse Events and Laboratory Abnormalities ([Appendix 3](#)). For AEs associated with laboratory abnormalities, the event should be graded on the basis of the clinical severity in the context of the underlying conditions; this may or may not be in agreement with the grading of the laboratory abnormality.

8.3. Investigator Requirements and Instructions for Reporting Adverse Events and Serious Adverse Events to Gilead

Requirements for collection prior to study drug initiation:

- After informed consent, but prior to initiation of study medication, the following types of events should be reported on the case report form (eCRF): all SAEs and adverse events related to protocol-mandated procedures.

Adverse Events

- Following initiation of study medication, all AEs, regardless of cause or relationship, pregnancy and other special situation reports, until 30 days after last administration of study drug must be collected/ reported to the eCRF database as instructed.
- All AEs should be followed up until resolution or until the adverse event is stable, if possible. Gilead Sciences may request that certain AEs be followed beyond the protocol defined follow up period.

Serious Adverse Events

- All SAEs, regardless of cause or relationship, that occurs after the subject first consents to participate in the study (ie, signing the informed consent) and throughout the duration of the study, including the protocol-required post-treatment follow-up period, must be reported to the eCRF database and Gilead Drug Safety and Public Health (DSPH) as instructed. This also includes any SAEs resulting from protocol-associated procedures performed after informed consent is signed.

- Any SAEs and deaths that occur after the post-treatment follow-up visit but within 30 days of the last dose of study drug, regardless of causality, should also be reported.
- Investigators are not obligated to actively seek SAEs after the protocol defined follow up period, however, if the investigator learns of any SAEs that occur after study participation has concluded and the event is deemed relevant to the use of IMP, he/she should promptly document and report the event to Gilead DSPH.
- All AEs and SAEs will be recorded in the eCRF database within the timelines outlined in the eCRF completion guideline.

Electronic Serious Adverse Event (eSAE) Reporting Process

- Site personnel record all SAE data in the eCRF database and from there transmit the SAE information to Gilead DSPH within 24 hours of the investigator's knowledge of the event. Detailed instructions can be found in the eCRF completion guidelines.
- If for any reason it is not possible to record the SAE information electronically, ie, the eCRF database is not functioning, record the SAE on the paper serious adverse event reporting form and submit within 24 hours to:

Gilead DSPH Email: [contact]
[contact]

- As soon as it is possible to do so, any SAE reported via paper must be transcribed into the eCRF Database according to instructions in the eCRF completion guidelines.
- If an SAE has been reported via a paper form because the eCRF database has been locked, no further action is necessary.
- For fatal or life-threatening events, copies of hospital case reports, autopsy reports, and other documents are also to be submitted by e-mail or fax when requested and applicable. Transmission of such documents should occur without personal subject identification, maintaining the traceability of a document to the subject identifiers.
- Additional information may be requested to ensure the timely completion of accurate safety reports.
- Any medications necessary for treatment of the SAE must be recorded onto the concomitant medication section of the subject's eCRF and the event description section of the SAE form.

8.4. Gilead Reporting Requirements

Depending on relevant local legislation or regulations, including the applicable US FDA Code of Federal Regulations, the EU Clinical Trials Directive (2001/20/EC) and relevant updates, and other country-specific legislation or regulations, Gilead may be required to expedite to

worldwide regulatory agencies reports of SAEs, serious adverse drug reactions (SADRs), or suspected unexpected serious adverse reactions (SUSARs). In accordance with the EU Clinical Trials Directive (2001/20/EC), Gilead or a specified designee will notify worldwide regulatory agencies and the relevant IEC in concerned Member States of applicable SUSARs as outlined in current regulations.

Assessment of expectedness for SAEs will be determined by Gilead using reference safety information specified in the investigator's brochure or relevant local label as applicable.

All investigators will receive a safety letter notifying them of relevant SUSAR reports associated with any study IMP. The investigator should notify the IRB or IEC of SUSAR reports as soon as is practical, where this is required by local regulatory agencies, and in accordance with the local institutional policy.

